1.0 Abbreviations

ABC	Activities-specific Balance Confidence
AE	Adverse Event
AKA	Above knee amputation
AMPnoPRO	Amputee mobility predictor without prosthesis score
ASCOT	Adult Social Care Outcomes Toolkit
BAMS	Basic Amputee Mobility score
BKA	Below knee amputation
CEAC	Cost-effectiveness acceptability curves
CONSORT	Consolidated Standards of Reporting Trials
CRF	Case Report Form
CUA	Cost-utility analysis
DMC	Data Monitoring Committee
EQ5D-5L	EuroQol 5 Dimensions (5L) score
GCP	Good Clinical Practice
HTA	Health Technology Assessment
ICER	Incremental cost-effectiveness ratio
ICH	International Council for Harmonisation
ISF	Investigator Site File
ISRCTN	International Standard Randomised Controlled Trial Number
MLLA	Major lower limb amputation
MRC	Medical Research Council
NICE	National Institute for Health and Care Excellence
NIHR	National Institute of Health Research
NVR	National Vascular Registry
PI	Principal Investigator
PIS	Patient Information Sheet
PPI	Patient and Public Involvement Group
PSS	Personal Social Services
QALYS	Quality Adjusted Life Years

QoL	Quality of life
REC	Research Ethics Committee
REDCAP	Research Electronic Data Capture
RNLI	The Reintegration to Normal Living Index
SAE	Serious Adverse Event
SAP	Statistical Analysis Plan
SCS	Socket Comfort Score
SIGAM	Special Interest Group in Amputee Medicine Score
SPARG	Scottish Physiotherapy Amputation Research Group
SWAT	Study Within A Trial
TAPES	Trinity Amputation and prosthesis experience score
TMG	Trial Management Group
TMF	Trial Master File
ТКА	Through-the-knee amputation
TSC	Trial Steering Committee
VAS	Visual Analogue Scale
WTP	Willingness-to-pay
YTU	York Trials Unit

2.0 Background and Rationale

Approximately 5,000 major lower limb amputations are performed each year in the UK (1), with numbers increasing due to the ageing population and rising prevalence of diabetes (2). Major lower limb amputation (MLLA) includes amputations conducted below the knee (BKA), above the knee (AKA) and through the knee (TKA). Costs to the NHS are approximately £200M/year (3), although this figure does not include the significant costs associated with formal and informal care, homecare visits, residential and nursing home placement. Following MLLA many patients do not return to independent living, with approximately one third of patients being discharged to a care facility (1).

Irrespective of the surgical procedure completed, MLLA has a significant impact on patient quality of life (4). A recent review concluded that the ability to walk successfully with a prosthesis following MLLA had the greatest positive impact on patient quality of life (4). AKA was negatively associated with quality of life due to increased difficulty in walking with a prosthesis (4). In addition to quality of life impacts, MLLA has substantial health implications, including anxiety, depression, altered body image and social discomfort, and the loss of general fitness and independence, which will contribute further to patient burden and healthcare costs (4, 5).

Patients not suitable for a BKA are usually offered an AKA, and less commonly a TKA. There are clear theoretical advantages from a longer residual limb which can be achieved with TKA, with end weight bearing capacity for rehabilitation and biomechanical advantage. However, there is little robust evidence to compare clinical and rehabilitation outcomes and complication rates of TKA and AKA (6). Where evidence is available, this is in the form of observational studies (3, 7) which have included small numbers of participants undergoing TKA compared to AKA and have failed to differentiate between AKA and TKA or between variations of TKA (3, 7). The heterogeneity of the available studies has resulted in variability in rates of uncomplicated healing, reoperation, successful ambulation, and survival but

A recent analysis of UK National Vascular Registry (NVR) and of the Scottish Physiotherapy Amputation Research Group (SPARG) registry data supports the suggestion of benefits with TKA (1, 8). TKA compared to AKA was found to be associated with fewer medical complications (20% Vs 27% respectively, p=0.005) and quicker discharge from rehabilitation services (99 Vs 133 days respectively, p=0.6) (8, 9), with more patients with TKA than AKA returning to their own home post procedure (51% Vs 43% respectively, p=0.049). No difference was seen between TKA and AKA in rates of wound healing (79% Vs 76% respectively, p=0.23). More people undergoing TKA required reoperation though this was not statistically significant (10% Vs 7%, p=0.06) (9). These results are however based on registry data, and hence important but unmeasured confounders cannot be adjusted for.

Both healthcare professionals and patients have suggested that a sufficiently powered RCT to evaluate TKA and AKA is required. A survey of UK vascular units indicated that TKA was performed in 78% of units but not all surgeons performed this procedure, with the main barrier being lack of evidence of a benefit (3), with separate qualitative data also highlighting the impact of lack of evidence on practice (10). Current guidelines also reflect the lack of evidence and support the need for further research in this area (11) (12). As part of a James Lind Alliance priority setting process for vascular patients with lower limb amputation, patients also highlighted this as a research priority, ranking improvement of clinical outcomes for patients following amputation as the third highest research priority.

There is a need for a high-quality study to determine if there are benefits of performing TKA. Definitive evidence to confirm or refute the potential advantages of TKA compared to AKA would greatly assist amputation multidisciplinary teams working with patients to decide upon the level of amputation that will confer greatest advantage and least risk of complications.

3.0 Aims and Objectives

3.1 Aim

To assess the clinical and cost effectiveness of TKA compared to AKA in patients requiring MLLA but who are unsuitable for a BKA.

3.2 Objectives

- To undertake a parallel group randomised controlled trial to compare the effects of TKA and AKA on quality of life and surgical and rehabilitation outcomes.
- To include a 12-month internal pilot phase to obtain robust estimates of recruitment rates, site set up and outcome data collection, and to evaluate intervention and trial process acceptability.
- iii) To undertake an integrated qualitative study to assess patient's lived experiences and acceptability of TKA and AKA and the trial.
- iv) To conduct a detailed economic evaluation to compare the cost-effectiveness of TKA and AKA to determine the most efficient provision for future care and resources.
- v) To explore how TKA may be implemented into clinical practice (if effective).

3.3 Hypothesis

Quality of life following TKA is superior to quality of life following AKA for patients requiring MMLA but who are unsuitable for BKA.

4.0 Trial Design

4.1 Design

The trial objectives will be addressed using a multicentre, two-arm, non-blinded, pragmatic, parallel group randomised controlled superiority trial.

The study will consist of a three-year recruitment phase, including the 12-month internal pilot phase, followed by the main recruitment period. Following collection of baseline measures, randomisation and treatment, all participants will be followed up for 24 months. Follow-up data will be collected from participants via a remote questionnaire every four months, at 4, 8, 12, 16, 20 and 24-months post randomisation.

The 12-month internal pilot will assess recruitment and retention and patient acceptability of both the intervention and trial processes. The pilot study will be set up in sites with existing surgical, rehabilitation and prosthetic experience of TKA, allowing additional time for other sites to receive training and support to implement or expand TKA services if required.

Semi-structured interviews will be conducted to include study participants, those who withdraw from the study and patients who decline to participate. The findings of these interviews will be used to inform aspects of trial design and delivery during this phase. These interviews will take place 8-10 weeks post-treatment.

To understand the longer-term impact of TKA and AKA on patient's lives and recovery, as part of the qualitative study, we will follow up a subgroup of 20-24 patients for up to 3 years, with interviews at 12, 24 and 36 months post-operatively.

A report will be provided to the funder at the end of the pilot phase and subject to their approval (assuming feasibility has been established) will proceed to the main trial.

4.2 Setting

Patients will be recruited from NHS hospitals within the UK that both provide MLLA care and have the facilities to support research activity. All participating hospitals will have the necessary resource and capability to perform both AKA and TKA surgery. A list of all study sites will be maintained by the trial management team and held in the trial master file.

4.3 Outcomes

4.3.1 Primary outcome

The primary outcome will be the quality of life (QoL) collected using the EuroQol 5 Dimensions (5L) score (EQ5D-5L) via remote questionnaire (telephone, electronic or postal) at 24 months post randomisation (Table 1 and 2). The EQ-5D-5L measures health-related quality of life in terms of 5 dimensions: mobility, ability to self-care, ability to undertake usual activities, pain and discomfort, anxiety and depression across 5 levels. The EQ-5D-5L will be scored according to the user guide (13).

4.3.2 Secondary outcomes

Secondary outcomes will be collected at baseline, within the hospital 5 days post procedure, during early assessment at a prosthetic centre (if applicable) and at 4 monthly intervals post-randomisation (4, 8, 12-, 16-, 20- and 24-months post-randomisation). These will include quality of life, surgical and rehabilitation outcomes, as well as longer term social and functional outcomes. Where possible, data collection will rely on routinely collected information in clinical notes to minimise the requirement for active input from participants (Table 2). To ensure timely collection of data a visit window of +/- 21 days will apply to each visit timepoint.

Quality of life

• EQ-5D-5L data collected at baseline and 4, 8-, 12-, 16- and 20-months post randomisation as recorded by the participant via remote questionnaire.

Surgical outcomes

- Perioperative blood loss estimated using the pre and post operative Haemoglobin (14) (15), alongside details of any blood products used in the perioperative period, as documented in the patient medical record.
- Planned or unplanned high observation or intensive care admission, collected from the patient medical record.
- Procedural pain using a Visual Analog Scale (VAS). The VAS consists of a 100-milimeter line representing a continuous scale. The line is anchored at both ends with the verbal descriptors 'No pain' (=0) and 'Worst imaginable pain' (=100). The outcome will be recorded by the participant at daily intervals over the first 5 days post procedure and will require the research team to visit them daily to collect this.
- Within hospital complications. Specifically referring to major adverse cardiovascular events, renal impairment and delirium. This information will be collected from the patient medical record.
- Impaired wound healing (including wound infection), as recorded in the patient medical record and via patient reported data.
- Return to theatre for revision surgery at either the same or a higher level of amputation, as documented in the patient medical record.
- 30-day mortality, as documented in the patient medical record.
- Total post operative length of stay, (from day of surgery to the day of discharge from treating hub) as documented in the patient medical record.
- The number of days alive and out of hospital, measured at 90 days through review of the patient medical record.
- The participant's destination on discharge from primary surgical bed. This will be derived from the patient medical record and recorded as own home/rehab facility/respite facility/residential care/nursing care.
- Contralateral limb outcomes including both minor and major amputation. This will be collected either via self-report at telephone follow up or collected from the patient medical record.

Rehabilitation outcomes

- Basic Amputee Mobility Score (BAMS): A score which can be used for daily assessment of the basic mobility of patients with leg amputation. This score will be used to assess the participants early mobility and will be measured by review of the participant's medical records at 5 days post procedure. Scores will be derived in alignment with the BAMS manual (16).
- Prosthesis assessment measured using the Special Interest Group in Amputee Medicine Score (SIGAM) (17): a single-item scale comprising six clinical grades (A-F) of amputee mobility. This score will be assessed from the review of the patient medical record at both the point of discharge from hospital and discharge from rehabilitation.
- Participant referral for prosthetic assessment, as recorded in the patient medical record it will be documented whether the participant has been referred or not.

If a participant is referred for prosthetic assessment:

- Amputee mobility predictor without prosthesis score (AMPnoPRO): an assessment tool designed to measure the functional status of lower-limb amputees without the use of a prosthesis (18). This will be recorded during the assessment of the initial visit at a prosthetic centre.
- The achieved expected level of rehabilitation. This will be the difference in score between the patients initial AMPnoPRO and final AMPnoPRO (non-prosthesis users) and AMPPro (prosthesis users) scores.

For participants issued with a prosthetic limb (to each be collected from participants remotely at 8-month intervals post randomisation):

- Trinity Amputation and prosthesis experience score (TAPES): consisting of 9 subscales which address psychosocial factors, activity restriction and satisfaction with the prosthesis (19). This score will be used to assess the participants experience of the prosthesis.
- Socket comfort score (SCS): an 11-point scale from 0-10, where 0 represents the most uncomfortable and 10, the most comfortable socket imaginable (20).
- Self-reported prosthetic wear time and usage.

Social care and long-term outcomes

The following measures will be collected from participants remotely at 8-month intervals post randomisation)

- Participant requirement for both paid/formal care and unpaid friends and family care.
- The Adult Social Care Outcomes Toolkit (ASCOT) SCT4 questionnaire: a multi-attribute utility index designed for the evaluation of long-term social care services, comprised of eight attributes that capture aspects of social carerelated quality of life (21).
- The number of participant self-reported falls (defined as the participant falling, tripping, stumbling or making contact with the ground) and associated complications. Participants will be asked to recall this information for the previous 4 weeks.
- Activities-specific Balance Confidence (ABC) scale: a questionnaire developed to assess the balance confidence of individuals when performing daily activities, on a wide continuum of less and more challenging activities (22).
- The Reintegration to Normal Living Index (RNLI): a measure to assess the reintegration into normal social activities for those with chronic illness. The 11 items within the index are each accompanied by a VAS anchored by phrases reflecting whether the statement describes the situation of the patient (23).
- Pain and phantom pain assessment assessed using a VAS (as previously described for the procedural pain outcome).

Health economics outcomes

• Resource use: a tailored questionnaire will collect data on healthcare resource use, prosthetics, private health services, and productivity loss.

Outcomes	Timepoint					
	Baseline		Pre/Peri/P ost Procedure	Discharge	Between randomisation and FU	Follow-up
Quality of Life (EQ5D)	x					x
Falls	х					Х
Frailty assessment	х					
Pain	х		х	х		Х
Perioperative blood loss			х			
High observation/intensive care admission				x		
Within hospital complications		R A	х	x		
Wound healing		N	х	х		Х
Further amputation surgery		0	х	x		x
30-day mortality						х
Total post-operative length of stay		S				x
Number of days alive and out of hospital (at 90 days)		T I				x
Discharge destination		N		x		
Contralateral limb outcomes	x					x
BAMS					х	
SIGAM					Х	
Prosthesis referral				х		Х
AMPnoPRO					Х	
Achieved expected level of rehabilitation					x	
Prosthetic wear time and usage					x	
Use of formal and informal care						x
Resource use						x
TAPES					X	
SCS					Х	
ASCOT						х
Balance (ABC)						х
RNLI						x

Table 1: Timeline of all outcomes to be collected

Table 2: The follow-up timeline for all outcomes which require activeparticipant input.

Timepoint*			Questionnaires		
Month 4	Quality of Life	Pain	ASCOT	Balance (ABC)	Wound
	(EQ5D)				Healing
Month 8	Quality of Life (EQ5D)	Pain	Falls	RNLI	TAPES⁺
Month 12	Quality of Life (EQ5D)	Pain	ASCOT	Balance (ABC)	Wound Healing
Month 16	Quality of Life (EQ5D)	Pain	Falls	RNLI	TAPES⁺
Month 20	Quality of Life (EQ5D)	Pain	ASCOT	Balance (ABC)	Wound Healing
Month 24	Quality of Life (EQ5D)	Pain	Falls	RNLI	TAPES⁺

*Visit window for data collection of +/- 21 days +Prosthesis users only

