10.3 Statistical analysis

All analyses will be described in detail in a statistical analysis plan (SAP) which will be finalised prior to the end of data collection and will be reviewed and approved by the TSC and DMC. The SAP will be made publicly available via the ISRCTN registry. Analyses will be carried out on a locked dataset and performed using two-sided statistical tests at 5% significance under the principles of intention-to-treat. All analyses will be conducted taking into consideration the reporting requirements of the Consolidated Standards of Reporting Trials (CONSORT).

The primary analysis will compare the EQ-5D-5L scores between groups using a covariance pattern mixed-effect linear regression model, incorporating all post randomisation time points.

Treatment group, time, treatment-by-time interaction, stratification factors and baseline covariates will be included as fixed effects. Participants will be included as a random effect accounting for repeated observations per patient. Estimates of the difference in EQ-5D-5L scores will be extracted for each time point (primary outcome at 24 months) and overall, with two sided 95% CIs. Three planned subgroup analyses will be performed by including the additional baseline variable, two- and three-way interactions between the subgroup, allocation and time point in the primary analysis: frailty; amputation aetiology and sex.

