11.0 Ethical arrangements

11.1 Risks and benefits

Both procedures will have the general surgical risks of wound infection, haematoma, bleeding, wound healing problems, seroma, heart attack, stroke, venous thromboembolism and death. Risks to participants from the intervention or control treatments are not increased through trial participation. Measures, such as emphasis on good practice and standardised protocols/care pathways throughout, are likely to reduce risk and could bring additional benefits. In the unlikely event that new

information arises during the trial that may affect participants' willingness to take part, the TSC will review this information to determine whether changes are required to the patient information leaflet. A revised consent form will also be produced if necessary.

Within the trial, participants allocated to receive a through knee amputation may experience a functional benefit to the longer residual limb and both an improved rehabilitation and resultant quality of life because of this procedure. As the purpose of the study is to provide evidence regarding this, this cannot however be guaranteed.

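### Limb-only and referred-only rehabilitation outcomes, and a gain score that changes instrument with prosthesis use, do not give intention-to-treat comparisons between the arms

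*Protocol*

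**What the plan says.** Protocol section 4.3.2, under rehabilitation outcomes, sets up two nested subsets.

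- **Referred participants.** AMPnoPRO and the score for the rehabilitation level achieved come under the condition "If a participant is referred for prosthetic assessment". The second is defined thus: "This will be the difference in score between the patients initial AMPnoPRO and final AMPnoPRO (non-prosthesis users) and AMPPro (prosthesis users) scores".
- **Participants with a limb.** TAPES, SCS and self-reported wear time and usage come under "For participants issued with a prosthetic limb (to each be collected from participants remotely at 8-month intervals post randomisation". The footnote to Table 2 describes the TAPES group differently: "Prosthesis users only".

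Referral is recorded for everyone: "it will be documented whether the participant has been referred or not". Issue of a limb is not listed as an outcome. SIGAM, BAMS, ABC, RNLI, falls, ASCOT and EQ-5D-5L carry no such condition.

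Section 10.3 places the analyses under one principle, "two-sided statistical tests at 5% significance under the principles of intention-to-treat", and makes no exception for these outcomes. Section 11.1 says that "participants allocated to receive a through knee amputation may experience a functional benefit to the longer residual limb", with better rehabilitation as a possible result. Section 2.0 links AKA to greater difficulty walking with a prosthesis.

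**The concern.** Whether a participant is referred, issued a limb or goes on to use it is decided after randomisation. The protocol's own rationale gives reasons to expect amputation level to influence these steps. Two problems follow.

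First, comparing arms only among people who have a limb compares groups selected by a process that treatment may alter. If one arm gets more marginal patients onto a limb, the average among its limb users can fall even when nobody has been harmed.

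Second, the gain score uses a with-prosthesis final score in users and a without-prosthesis final score in non-users. Any difference between the two instruments at equal function enters the between-arm contrast in proportion to the difference in prosthesis use.

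Rehabilitation is the route by which TKA is expected to improve quality of life. A misleading result here would cloud the explanation of the primary result, though it would not change that result.

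**Working it through.** The protocol gives no figure to reproduce on this point: no issue or use rates, no AMP scale, and no offset between AMPnoPRO and AMPPro. Every rate, correlation, wear time and offset below is an assumption. The calculations show only what can happen.

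**1. Wear time.** Assume 30% of AKA participants use a limb for 8 h/day. Assume TKA has the same 30% at 8 h/day plus a further 15% who wear it for h hours.

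- Users only: TKA mean = (0.30 × 8 + 0.15 × h) / 0.45, against 8.0 for AKA. The difference is (h − 8) / 3.
- All participants, non-users at 0: TKA mean = 0.30 × 8 + 0.15 × h, against 0.30 × 8 = 2.40. The difference is 0.15 × h.

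| h | Users only, TKA v AKA | Difference | All, TKA v AKA | Difference |
|---|---|---|---|---|
| 3 | 6.33 v 8.0 | −1.67 | 2.85 v 2.40 | +0.45 |
| 6 | 7.33 v 8.0 | −0.67 | 3.30 v 2.40 | +0.90 |
| 8 | 8.0 v 8.0 | 0 | 3.60 v 2.40 | +1.20 |

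The two analyses disagree in sign whenever the additional users wear the limb for more than 0 but less than 8 h.

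**2. Limb-only scores (TAPES, SCS).** Assume no true effect on the score, limbs going to the fittest fraction p of each arm, and fitness correlated with the score at ρ. Mean fitness in the top fraction p of a standard normal is φ(z)/p, with z = Φ⁻¹(1 − p). This gives 1.400 at 20%, 1.159 at 30%, 0.966 at 40% and 0.798 at 50%. The bias is ρ × (TKA value − AKA value).

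| Issued, AKA v TKA | ρ = 0.3 | ρ = 0.7 |
|---|---|---|
| 30% v 40% | −0.06 SD | −0.14 SD |
| 30% v 50% | −0.11 SD | −0.25 SD |
| 20% v 40% | −0.13 SD | −0.30 SD |

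Minus means against TKA. With equal issue rates the bias in this model is zero. If AKA had the higher rate, the sign would reverse.

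**3. AMP gain score.** Let k be the AMPPro reading minus the AMPnoPRO reading at equal function. Let qT and qA be the proportions of *referred* participants in each arm whose final score is AMPPro. With no true change, the between-arm difference in mean gain is k × (qT − qA).

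- 30% (AKA) v 40% (TKA), k = 1 to 4: 0.1 to 0.4 points.
- 30% v 50%, k = 1 to 4: 0.2 to 0.8 points.
- Negative k gives the same sizes with the opposite sign. If k = 0 or qT = qA, the difference is zero.

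Selection through referral comes on top of this. The denominator is those referred, so rates among all randomised participants cannot be carried over to it.

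**The case against.** The strongest reply has four parts.

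**The analysis belongs to the SAP.** Section 4.3.2 says who is measured; it does not say that TAPES, SCS or wear time will be tested between arms. A SAP could call them descriptive or code wear time as zero. This stands in part. But the subsets and the two-instrument definition are fixed in the protocol, and the intention-to-treat statement in section 10.3 does not exempt them.

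**Collection has to be restricted.** Socket comfort and satisfaction with a prosthesis cannot be measured without one. This stands. The fault would lie in comparing arms on these scores as if the groups were as randomised, not in collecting them.

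**The mixed score may be intended.** AMPnoPRO is a mobility predictor, so the outcome could set a predicted level against the level reached in the state in which the patient lives. What the limb adds would then belong to the effect. The text allows this reading, so the complaint that no expected level enters the score cannot be pressed. The reading still needs the two instruments to share a scale, and none is given.

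**Unrestricted measures exist.** SIGAM is graded without regard to referral or issue, and ABC and RNLI are collected without that condition. This stands, and it makes the fix easier.

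A reader might also infer that the AMP score favours whichever arm has more users. The documents do not support that: it requires AMPPro to read higher at equal function, and no offset or scale is stated.

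**Conclusion.** The point holds for this group of secondary outcomes. Wear time, TAPES and SCS are conditional on limb issue, the AMP gain is conditional on referral, and its instrument is conditional on use. All three conditions arise after randomisation and may be affected by amputation level. Between-arm comparisons on these outcomes are therefore not intention-to-treat and can mislead.

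Neither direction nor size can be fixed from the documents. The wear-time reversal, the 0.06 to 0.30 SD selection bias and the 0.1 to 0.8 point AMP shift rest wholly on assumed inputs. It would be too strong to say that these outcomes will point the wrong way, or that they are biased towards a named arm. The EQ-5D-5L primary outcome and the unrestricted secondary outcomes are untouched. The change is worth making because a selection effect that can reverse a sign is cheaply avoided.

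**What to change.** 1. List prosthesis issued (yes/no) as an outcome in all randomised participants, beside referral. Issue must already be known to decide who receives TAPES.
2. Analyse wear time in all participants alive at the time point, entering 0 for those without a limb or not using it. The cost is a zero-inflated outcome, which needs a suitable model or summary.
3. Present TAPES and SCS as descriptive results in those issued a limb. Reconcile the text of section 4.3.2, which refers to limb issue, with the Table 2 footnote, which refers to use; someone issued a limb may not use it.
4. Do not pool AMPnoPRO and AMPPro change in one between-arm comparison. Report the AMP scores descriptively by instrument and use the SIGAM grade to compare mobility between arms. Use within-instrument AMPnoPRO change only if a final AMPnoPRO is already recorded in users. Otherwise it would be missing for them or need an added assessment, and it would in any case remain conditional on referral.

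Items 1 to 4 change outcome definitions and analysis wording and need no new participant visits.
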